3. STUDY DESIGN

We will conduct a pragmatic two-arm, parallel groups 36-week multi-site randomized controlled single blind trial of SBIRT-PM. Drawing from VISN1 medical centers, we will randomize 1100 post-911 era Veterans applying for MSD-related compensation to either: 1) SBIRT-PM, a single phone-delivered session followed by up to three calls in a 12-week period and an additional call in the 12-32-week period; or 2) usual care (UC). Primary outcomes will be change in pain severity (BPI Composite severity) and change in the number of substances categorized as requiring intervention (ASSIST). The two primary outcomes will be measured by self-report at 12- and 36- week follow-ups. The self-report BPI and ASSIST measures will be completed with the Research Assistant by

telephone with the patient's responses entered directly into REDCap. The Research Assistant conducting all study assessments will be blinded. Secondary outcomes will include non-pharmacological pain management service utilization, pain interference with life activities (BPI), overall pain (PEG), overall health (EQ-5D-5L), use severity for individual substances generated by the ASSIST, and toxicology results for individual substances. The trial will include cost-effectiveness and budget impact analyses.

Study Settings.

The study will occur within the eight VISN1 VA medical centers (VAMC) located across six New England States. Each site provides MSD-related compensation examinations, addiction/mental health treatment, and a variety of non-pharmacological pain treatments.

The medical centers are:

1. Bedford VAMC
2. Boston Healthcare System
3. Central Western Massachusetts
4. Connecticut Healthcare System
5. Maine Healthcare System
6. Manchester VAMC
7. Providence VAMC
8. White River Junction VA

Feasibility of Recruiting a Sufficient Number of Veterans Who Meet Inclusion/Exclusion Criteria:

As noted in the completed SBIRT-PM RCT, in only 21 months of recruiting, 1017 examinations (for 1014 unique Veterans) were scheduled for service-connection examinations for back, neck, knee, or shoulder. Over the 32 months of recruitment for the proposed study, this would come to 1448 potentially eligible Veterans at VA Connecticut. To extrapolate from these values to the number of eligible participants we could expect at each of the other seven sites within VISN 1, we used VBA reports of new service-connection examinations requested at each of the other sites for back/neck/knee/shoulder. We then assumed the same proportion at each site would be eligible as were at the Connecticut site.

At VA Connecticut, 257/1014 Veterans met eligibility criteria and enrolled (a 24.3% enrollment rate). The proposed study is likely to enroll at least as high a percentage, and probably higher because: (1) enrollment by phone asks less of Veterans than enrollment in person required in the prior study; and (2) there are fewer inclusion/exclusion criteria in the proposed study. Conservatively assuming the 18% enrollment rate in the UG3 pilot (with only one call to many participants) yields 1862 exceeding the study's randomization goal of 1100. The large sample allows for study completion should recruitment lag at one or more sites.

The large numbers of readily recruitable Veterans in a single VISN speaks to how many Veteran are at risk and engageable at their service-connection examinations.

VISN 1 VA Medical Center	Projected Number of Post-9/11 Veterans Scheduled for MSD Service-Connection Examination over 32 Months of Study
VA Boston	2478
VA Connecticut	1448
Providence, RI	1584
Manchester, NH	1275
Togus, ME	1493
Bedford, MA	744
White River Junction, VT	677
VA Central Western Massachusetts HCS	650
Total	10349

Sources of Materials

Veterans sources of materials:

Information to be collected includes:

1. Veteran questionnaire responses entered into VA REDCap
2. Nail clipping toxicology tests
3. Audio recorded SBIRT-PM sessions
4. Information from the electronic health record (EHR), including the record of the Compensation examinations and service connection determination
5. Service use data from central VA databases

VA Staff sources of materials:

Information to be collected includes:

1. Responses to Relational Coordination Survey
2. Digital recordings of interviews and transcriptions

Assessment Procedures.

A research assistant, blind to study condition, will conduct baseline, 12- and 36-week participant assessments by telephone. Veterans will be instructed during the assessments not to tell the research assistant if they are receiving study counseling. To determine if the blind was maintained, the research assistant will be asked in what condition each Veteran was assigned. In the initial RCT of SBIRT-PM reported in the Preliminary Studies, the accuracy of research assistants' guesses about treatment condition assignment were almost exactly at chance (52%). We will abstract data from the VA electronic health record (EHR) when possible.

Procedures to Collect Self-Report Data from Veteran Participants.

The self-reported assessment will be conducted by phone. Baseline assessment will be conducted as soon as possible after enrollment, and follow-up phone assessments will be conducted approximately 12 and 36 weeks after randomization. Participants will receive a reminder call or text/email message prior to study appointments (e.g., "your follow-up phone interview with our research study is Monday, December 11th at 1:30. Please call [Name] at xxx-xxx-xxxx if you need to reschedule"). If a participant misses a scheduled appointment, the research assistant will call to reschedule. Participants will be asked at the beginning of enrollment for the names and telephone numbers of three

people who can find them if the research assistant has difficulty reaching them. These people will be contacted if the research team is unable to reach the Veteran within a three-week period.

Procedures to Collect Self-Report Data from VA Staff Participants

Each Site-PI will identify a list of 7-10 stakeholders (providers in primary care clinics, pain service clinics, administration, and Compensation & Pension clinics) at their site. At the end of the study (after recruitment and follow-up appointments are complete), our qualitative expert and her team will contact stakeholders by email, inviting them to participate in a semi-structured interview designed to better understand how pain services are conducted at their site and how staff at each site communicate with other clinics regarding Veteran referrals for pain services. The qualitative expert and her team will place a follow-up phone call to stakeholders to schedule an interview. Interviews will last approximately 30 minutes, and will utilize a semi-structured interview guide. Interview responses will be audio-recorded and professionally transcribed by a VA approved transcription service for later qualitative analysis.

Stakeholders will also be invited via email to complete a Relational Coordination survey, administered through VA REDCap. Survey responses will be collected confidentially and stored in VA REDCap in the secure VA environment.

Procedures to Collect Data from the VA Electronic Health Record.

VHA databases in the Corporate Data Warehouse hold patient demographics, diagnoses, and encounter information from all Veterans who have received services from anywhere in VHA. Veterans who are scheduled for a service-connection examination (all study participants) have a medical record with VHA. The encounters indicate a provider, service provider, diagnoses addressed, and clinic in which services were delivered (e.g. mental health, substance use, primary care, pain clinic). The diagnosis and service-use data are not comprehensive for Veterans who have not been receiving their care at VA, but positive findings such as treatment encounters and diagnoses reflect clinical care/evaluations and their charting by providers.

Costs Estimation Procedures.

We will use the customized Resource Allocation Worksheet to estimate the costs of delivering SBIRT-PM from the perspective of the providers (i.e., both the VISN and hospital). Cost estimation for VA services used by Veterans during the 36-week study period will be assessed using national VA administrative databases. Data on service use at the individual patient level will come from the VA National Patient Care Database (NPCD), which includes information on all inpatient and outpatient encounters at VA facilities. Costs for these services will be computed using the VA Average Cost Database, developed by the Health Economics Resource Center (HERC). The Average Cost Database assigns an average cost to each inpatient admission and outpatient visit in VA. Costs are based on Current Procedure Terminology (CPT) codes and can be linked to unique records in the NPCD.

Costs for VA services used by Veterans during the 36-week study period will be assessed using national VA administrative databases. Data on VA service use at the individual patient level will come from the VA National Patient Care Database (NPCD),

which includes information on all inpatient and outpatient encounters at VA facilities. Costs for these services will be computed using the VA Average Cost Database, developed by the Health Economics Resource Center (HERC). The Average Cost Database assigns an average cost to each inpatient admission and outpatient visit in VA. Costs are based on Current Procedure Terminology (CPT) codes and can be linked to unique records in the NPCD. Costs incurred by VA for community care will be obtained from databases tracking payments to community providers.

Procedures to develop a new natural language processing (NLP) algorithm that identifies use of non-pharmacological pain management services

To comprehensively identify pain-related treatment delivered to study participants, we will validate and extend existing natural language search algorithms, using previously-described procedures, to identify current use of a comprehensive set of pain treatments including those *not covered by the existing algorithms*. Those modalities will be drawn from a review of modalities used by Veterans for pain treatment and those offered in VISN 1. Algorithm development will be informed by our prior experience with this study design. We will design algorithms to maximize positive predictive value (at the expense of sensitivity) to avoid the risk of including false positives that are not randomly distributed (e.g., refused treatment referrals). The NLP extraction target will be current use of the modality. Particular attention will be paid to excluding pain discussions that do not represent treatment because they were obtained in the course of routine medical history reviews. Algorithm development involves extracting relevant snippets that mention a particular pain treatment, establishing a valid classification system for current use of that pain treatment, and optimizing the machine learning algorithm to identify current use of that treatment.

Extracting relevant snippets: In brief, terms related to each of the pain treatments (i.e. therapy keywords) will be generated by the investigative team. For example, for physical therapy, terms might include “physical therapy,” “PT,” or “physical therapist.” A simple algorithm will identify these terms, along with the 10 preceding and 10 following words. By our observation, a 20-word window is sufficient to capture most of the relevant context, and also allows for fast review of multiple records. The algorithm will be modified using Boolean terms (e.g. physical NOT physical exam). We will refine the search terms and extract 20+ word snippets using the Voogo clinical data search engine.

Establishing a valid classification system for use of a pain treatment modality: The investigators will develop annotation guidelines for classifying snippets as representing current service use (e.g. of physical therapy services as no/yes/probably). One challenge is that the documentation of temporal information varies in specificity. We will classify the temporal information into several categories based on the onset and duration attributes. For instance, usage with a non-specific past start and end time (e.g. “patient used physical therapy before”) will be considered to be past usage, usage with no specific past start but no end time (e.g. “patient has been going to a physical therapist”) will be considered current for the time of documentation, usage with specific start and end time will be considered current for the time it specified, etc. The annotation guidelines will be revised and then tested on 100 snippet samples until a kappa of 0.75 is reached between the two experts.

Optimizing the machine learning algorithm to identify use of a pain treatment: We will then randomly select 500 text snippets containing terms per type of pain therapy from all retrieved notes from primary care and perform human review based on the annotation guideline described above. Annotation work will be carried out using the Visual Tagging Tool (VTT). This set of annotated data will be added to our existing set of annotated data (n=3000) and serve as the new gold/reference standard for machine learning and training. We will apply a machine learning algorithm, Support Vector Machine (SVM), to identify current use of pain therapy, optimizing for highest positive predictive values (PPV). Informed by our prior experience, we will use therapy keywords, n gram (n consecutive words), note type, and temporal information as features in the classification of current use. Temporal information will be extracted using a prior method developed and tested by [name].⁸⁸

To assess the NLP performance, we will perform 10-fold cross validation, which partitions the entire annotated sample into 10 random sets with equal size, uses 9 sets for training and 1 for testing, and repeats 10 times. Our target PPV is $\geq 90\%$, which is very likely to be reachable because: 1) the specificity of the test has been set high (at the cost of sensitivity); 2) the usage level (prevalence) of the primary non-pharmacologic modalities for chronic pain treatment is high which increases PPV; 3) we achieved 89% PPV in our work on a small set of modalities. We will apply machine learning methods we trained using previously acquired annotated data such as Support Vector Machine and Random Forest, and will use an ensemble learning step called Stacking,⁸⁹ in which a learning algorithm combines the results of several other learning algorithms, if the separate programs' performance fails to reach the target positive predictive value. In the unlikely event that the PPV is not reached for a particular CIH modality, that modality's assessment will be conducted by the other two available methods (self-report and EHR codes).

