Data for the study are drawn from patient self-report, VA electronic medical records of VA and community care, and the C&P examination. Veterans requesting a Compensation & Pension evaluation for knee, shoulder, neck or back pain may or not be receiving services from the VA. Persons who get all their care outside of the VA will not have readily accessible medical records, while those persons who get some care in the VA but are sent out to community care for distinct services (such as non-pharmacological pain management) will have medical records of both types of care. In addition, those veterans who had not used any VA services prior to their C&P request may then enter VA care following their C&P exam and will have EMR available only in the follow-up period. The lack of EMR data of non-users of the VA will affect both the intervention or control arms of the study, and there is no reason to believe its effect will be differential.

Acknowledging the variability in availability of EMR information, all subjects will have self-reported and C&P data regarding service use as well as diagnoses. We will examine the concordance of self-reported and EMR-obtained information to estimate the impact of having no EMR data in the non-users of the VA. We will conduct a sensitivity analysis sub-setting the analyses only to those persons with available EMR (as well as self-reported and C&P data).

Cost-Effectiveness Analysis

The relative cost-effectiveness of SBIRT-PM will be assessed using both incremental cost-effectiveness ratios (ICERs) and cost-effectiveness acceptability curves (CEACs). ICERs and CEACs will be calculated from the provider (i.e., VISN and medical center) perspective. Using the cost estimates described in the Assessment subsection, we will calculate ICERs for minimal clinically important differences (MCID) between baseline and week-36 assessments in three primary outcomes: self-reported pain, risky alcohol use, and morphine-equivalent doses of opioid analgesic medication use.

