To illustrate the uncertainty associated with ICER point estimates, cost and effect estimates of SBIRT-PM will be bootstrapped (with 2,000 replicates) to produce confidence intervals around the ICERs and to produce CEACs for each outcome measure.¹⁸⁸ CEACs quantify the uncertainty in the cost-effectiveness analysis by showing the probability that the intervention is cost-effective with respect to any given threshold value.¹⁸⁸⁻¹⁹⁰ Intuitively, as the threshold value of a MCID in a given outcome increases, the strategy that produces that effect most efficiently becomes increasingly more likely to be the most cost effective, even though incremental costs are incurred. Similarly, as the threshold value of a MCID in a given outcome decreases, the strategy that has the lowest cost becomes increasingly more likely to be the most cost-effective. Finally, sensitivity analyses will be conducted to determine the robustness of the cost-effectiveness results to alternative assumptions about a wide variety of implementation parameters (e.g., cost of inputs).

Budget Impact Analysis.

To demonstrate the financial feasibility of adopting SBIRT-PM, a budget impact analysis will be conducted. The per-person cost of SBIRT-PM will comprise the cost of delivering the intervention plus the cost of the VA-funded services used by the participant in the SBIRT-PM condition over and above the cost of those used by individuals in UC, minus the yearly patient allocation (VERA dollars) assigned to that participant. The total projected yearly cost to a given medical center of SBIRT-PM will be the per-person cost times the total number of Veterans applying for compensation and pension for a musculoskeletal condition times the expected rate of uptake.

Analyses of NLP Algorithms

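### The plan states no estimator for incremental VA cost and no adjustment for pre-randomisation VA cost, which gives up precision in the ICERs, acceptability curves and budget impact

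*Combined protocol and SAP*

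**What the plan says.** Both paragraphs under Costs Estimation Procedures (section 3) confine VA service cost to the 36 weeks of the study: "Cost estimation for VA services used by Veterans during the 36-week study period will be assessed using national VA administrative databases". Service use comes from the national patient care database, "which includes information on all inpatient and outpatient encounters at VA facilities", and is priced with the VA average cost database. Community care has its own source: "Costs incurred by VA for community care will be obtained from databases tracking payments to community providers". No look-back before randomisation is mentioned.

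In section 9.6, Cost-Effectiveness Analysis, these costs are the cost input to the ICERs, from the perspective of the VISN and medical center. On estimation, the plan says only that "cost and effect estimates of SBIRT-PM will be bootstrapped (with 2,000 replicates) to produce confidence intervals around the ICERs" and the acceptability curves. The economic sensitivity analyses vary implementation parameters such as input costs. In the Budget Impact Analysis, the service term for SBIRT-PM is the cost of VA-funded services "over and above the cost of those used by individuals in UC", and the VERA allocation is then subtracted.

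On the population, section 9.6, Sources of data, says that claimants "may or not be receiving services from the VA", and that some will enter VA care only after the compensation examination. The urn factors (sections 6.2.2 and 9.2) are site, sex, race, ethnicity and illicit drug use. Prior VA use is not among them.

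**The concern.** Objective 3 and the budget impact both depend on a difference in mean cost. That cost covers every VA inpatient and outpatient encounter, while the intervention is small: 60 + 3 × 20 = 120 minutes of planned counselling, plus at most one further call. Variation in all-cause cost may therefore dominate the numerator of every ICER.

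VA cost before randomisation is an obvious candidate for explaining part of that variation. The corporate data warehouse is said to "hold patient demographics, diagnoses, and encounter information from all Veterans who have received services from anywhere in VHA", so prior use can be retrieved without contacting participants. Neither the randomisation nor the analysis plan uses it. The clinical side is treated differently: the economic effects are changes from baseline, and the pain model controls for baseline. The covariates in section 9.6 are listed with the clinical outcome models, and nothing extends them to cost.

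At stake are the width of the cost interval and the credibility of an incremental cost that could partly reflect which arm happened to receive more established or high-cost VA users.

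**Working it through.** **The plan's own figures.** The documents give no cost mean, cost SD, incremental cost or correlation over time, so there is no cost figure to reproduce. The sample size does reproduce: d = 0.25, two-sided alpha 0.025 and power 0.90 give 398 per group against the stated 400, and 400 / 0.73 = 548 per group, 1096 in total. Only the randomised 1100, or 550 per arm, is carried forward, because administrative cost does not depend on completing interviews.

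**Assumed inputs.** Correlation r between pre- and post-randomisation cost on the raw scale: 0.2 to 0.7. Ratio of cost SD to mean: 1 to 3.

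**Unadjusted precision.** SE of the difference = SD × √(2/550) = 0.060 SD. The 95% half-width is 1.96 × 0.0603 = 0.118 SD. At SD/mean of 1, 2 or 3 this is 11.8%, 23.6% or 35.5% of mean cost.

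**Effect of adjustment.** Adjusting for baseline cost multiplies the SE by √(1 − r²). The equivalent sample size per arm is 550 / (1 − r²). A chance baseline imbalance of one SE moves the unadjusted difference by r × 0.060 SD.

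| r (assumed) | SE factor | SE reduction | 95% half-width (SD) | Equivalent n per arm | Shift per 1-SE imbalance (SD) |
|---|---|---|---|---|---|
| 0.2 | 0.980 | 2% | 0.116 | 573 | 0.012 |
| 0.3 | 0.954 | 5% | 0.113 | 604 | 0.018 |
| 0.5 | 0.866 | 13% | 0.102 | 733 | 0.030 |
| 0.7 | 0.714 | 29% | 0.084 | 1078 | 0.042 |

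At r = 0.5 the half-widths of 11.8%, 23.6% and 35.5% become 10.2%, 20.5% and 30.7% of mean cost.

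**Check with skewed costs.** A simulation used 550 per arm, lognormal costs, no true arm difference, and 0%, 30% or 50% of participants with zero prior cost (all assumed). The mean unadjusted difference was −0.04, 0.03 and −0.04 of its SE, with a Monte Carlo error of 0.03, so there was no sign of bias. With no zeros, the log-scale correlation was 0.8² / (0.8² + 0.9²) = 0.44, but the raw-scale correlation averaged only 0.29. Across the three settings it was 0.19 to 0.29, and adjustment cut the SE by 2% to 4%. The zeros were placed at random, so prior-user status carried no information in this set-up.

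A second set of simulations adjusted for prior cost and prior-user status, with 20% to 50% prior non-users and half of them entering VA care (assumed). The SE fell by about 1% to 7% at realised correlations of 0.17 to 0.28, 4% to 9% at 0.31 to 0.42, 14% to 22% at 0.50 to 0.59, and 26% to 34% at 0.67 to 0.76. The gain follows the correlation, which is the quantity nobody can read from the documents.

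**The case against.** The strongest reply is that nothing here is invalid. Assignment is randomised, so an unadjusted cost difference is unbiased, and chance imbalance is part of the sampling variation that the bootstrap intervals and acceptability curves already express. That stands: the point concerns efficiency and robustness.

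Three stronger readings are tempting and should be resisted.

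- A reader might infer that costs will be compared as raw arm means. The plan does not say so. It bootstraps cost estimates without defining them, which is compatible with adjusted or unadjusted estimation. Only the budget impact wording resembles a simple difference.
- A reader might infer that the databases already hold prior cost for everyone. Section 3 does say that all participants have a VHA record, but it also says service-use data are incomplete for Veterans treated elsewhere. Section 9.6 says some will have records only in follow-up. Community-care payments also sit in separate databases. From the provider's perspective, no VA use is a true zero cost, but the plan has to state that rule.
- A reader might take prior cost to be a strong predictor. The documents give reason for doubt: section 2.2 notes that service connection brings priority VA care, so claimants are at a point where their VA use may change.

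It is also fair to object that adjusting the service term alone leaves the VERA term of the budget impact untouched. The fix has to address this.

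**Conclusion.** The point holds as a cheap improvement to an under-specified analysis. Two gaps are plain on the page: the estimator of incremental cost is not stated, and no pre-randomisation cost enters the ICERs, acceptability curves or budget impact. Bootstrapping an undefined estimator 2,000 times does not define an analysis, so the first gap needs closing whatever is decided about adjustment.

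The documents do not support a claim of bias. The cost of the second gap is lost precision: an SE about 2% to 29% larger than need be, relative to the unadjusted SE, if the raw-scale correlation is 0.2 to 0.7. That range is an assumption, and its low end is realistic given skewed costs and new entrants to VA care. The conclusion also assumes that prior VA cost can be retrieved over a common window, with non-use counted as zero.

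**What to change.** In section 3, Costs Estimation Procedures, extend the planned VA encounter and cost extractions, and the community-care payment extraction, back over a fixed window ending at randomisation (for example 36 weeks). State that participants with no VA use in that window have a VA cost of zero, and define a prior-VA-user indicator.

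In section 9.6, define incremental service cost as the arm coefficient from a linear regression of cost on arm, adjusting for pre-randomisation cost, prior-user status, site and the other urn factors. Refit it in each of the 2,000 bootstrap replicates. Use this estimate in the ICERs, the acceptability curves and the service-cost term of the budget impact, and report the unadjusted difference alongside. State whether the VERA term is handled in the same way, so that the net figure does not mix adjusted and unadjusted parts without saying so.

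Date the change in the SAP, because sections 6.2.3 and 9.2 say the statistician is unblinded.

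The cost is a longer look-back in extractions already planned, some extra analysis and SAP wording, with no participant contact. Section 6.1 already schedules baseline VA pain-service use from the health record, so a baseline extraction is not new in kind. The downside is that the gain may be small.

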4.2 Exclusion Criteria

1. reports inability to participate during the study enrollment call;
2. received three or more non-pharmacological pain treatment modalities within the last 12 weeks from VA (modalities are: (1) acupuncture (2) rehabilitation therapies (3) Manipulation (4) Massage (5) Yoga (6) Tai Chi/Qigong (7) exercise (8) Biofeedback (9) Hypnosis/Hypnotherapy (10) Guided Imagery (11) Meditation (12) Psychotherapy/Counseling (13) Reiki (14) teaching about coping with pain (15) other treatment for pain);
3. participation in another PMC3 study as evidenced by a research protocol alert for that study at the time the study invitation letter is mailed.

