Research staff will describe the purpose of the survey and interview prior to administering these assessments. Participating VA staff members will be encouraged to ask any questions and have the option to discontinue participation without prejudice. They will be approached by people other than their direct supervisors.

After a brief reiteration of the study purpose, the interviewer will confirm consent to record the interview for transcription and analysis purposes before proceeding.

Screening for medical record review to develop the natural language processing (NLP) algorithm for pain-related treatments.

A computer algorithm will be used to identify key terms (e.g. “physical therapy” along with the 10 preceding and 10 following words: a snippet. Snippets of chart data will be identified that contain pain-related treatment keywords and surrounding text will be identified from electronic medical records from up to 10,000,000 (approximately number of Veterans with medical records). As such, although not specifically queried for PHI, a snippet might contain some PHI such as a visit date and doctor’s name. All of the work with the snippets is done in the VINCI data analysis environment behind the firewall in the VA. Access to the VA network and VINCI are password protected and only accessible at the VA or through remote access with an approved device. These snippets will be reviewed to identify approximately 700 snippets per pain treatment modality (100 for developing annotation and 600 for validating the algorithm using the developed annotation).

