We will identify the use of non-pharmacological pain modalities through self-report from the participants as well as two different approaches to the extraction of healthcare utilization data from electronic medical records. Medical record extraction of 1.) Structured data - stop codes indicating use of these modalities, and 2.) Unstructured data - domains identified in the application of the NLP method to the medical record data of study participants. Two independent researchers will identify words/snippets that suggest use of specific non-pharma modalities and rate enough snippets to have software reliably generate an algorithm to rate all patients included in the study on each modality (machine learning). As we expect false positive reports of use of a modality to be unlikely, identification of use during an assessment period by any of the three methods (self-report, medical record stop codes and NLP) will be considered use. The agreement between these different measures will be described by cross-tabs.

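### The 90% PPV target for the NLP measure is tested per snippet, but use is scored per participant, so the premise that false positives are unlikely is not established, overall or by arm.

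*Combined protocol and SAP*

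**What the plan says.** **Validation (Section 3, NLP procedures).** Annotators will "randomly select 500 text snippets containing terms per type of pain therapy from all retrieved notes from primary care" and classify each for current use. These are added to 3000 existing annotations, and performance is judged by "10-fold cross validation, which partitions the entire annotated sample into 10 random sets with equal size". Section 4.3 says the snippets come "from electronic medical records from up to 10,000,000" Veterans, so the development sample is VA-wide. The target is at least 90%. One reason given for expecting to reach it is that "the usage level (prevalence) of the primary non-pharmacologic modalities for chronic pain treatment is high which increases PPV"; another is that "we achieved 89% PPV in our work on a small set of modalities". A modality that misses the target falls back on self-report and record codes.

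**Use in the trial (Section 9.6, Analyses of NLP Algorithms).** The algorithm rates every study patient on each modality. A positive from any one of self-report, stop codes or NLP counts as use in that period. The stated ground begins "As we expect false positive reports of use of a modality to be unlikely". The only check described there is cross-tabulation of the three methods.

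**Population (Section 4.2).** Veterans who "received three or more non-pharmacological pain treatment modalities within the last 12 weeks from VA" are excluded.

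**Role of the measure.** Service use is a secondary outcome (Section 9.5.2) and a proposed mediator for the pain and substance use outcomes (Section 1.1).

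**The concern.** A PPV measured on isolated snippets does not determine a PPV measured on people. A participant may have no snippet for a modality, or several. If one snippet classified as current use is enough, each further snippet from a non-user is another chance of a false score. Under the any-of-three rule, a negative self-report cannot overturn it. The fallback does not protect against this, because it is triggered by the same snippet-level figure.

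The error may also differ by arm. Section 3 names refused referrals as a source of non-random false positives. SBIRT-PM produces text of a related kind. Its counselors write record notes asking providers to consider consults (Section 5.1) and listing the referrals the Veteran would like (Section 5.2). Interest without uptake is not use. These notes exist in one arm only, and nothing excludes them from the text the algorithm reads. Misclassification of this kind could look like a treatment effect on service use, and then like mediation.

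**Working it through.** **The plan's own figure.** The 90% target cannot be reproduced, because the documents give no sensitivity, specificity or snippet-level prevalence. The only related figure is the earlier 89%, which is just below the target.

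**Assumed inputs (none is in the documents).** Snippet sensitivity s = 0.70. Share of validation snippets showing true current use p0 = 0.30, with 0.50 as an alternative. Share of participants who truly use a modality π = 10% to 30%. Share of non-users with any keyword snippet g = 10% to 100%. Each user has k = 3 use and 3 non-use snippets; each non-user with any snippet has 3. Errors are independent, and one positive snippet suffices.

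**Step 1. Snippet false-positive rate implied by a PPV of 0.90.**
f = s × p0 × 0.1 / [0.9 × (1 − p0)]
p0 = 0.30: f = 0.70 × 0.30 × 0.1 / (0.9 × 0.70) = 0.033
p0 = 0.50: f = 0.70 × 0.50 × 0.1 / (0.9 × 0.50) = 0.078

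**Step 2. From snippet to participant (p0 = 0.30, k = 3).**
Non-user with snippets scored as user: F = 1 − (1 − 0.033)³ = 0.097
User scored as user: S = 1 − 0.30³ × (1 − 0.033)³ = 0.976

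**Step 3. Participant-level PPV** = πS / [πS + (1 − π) × g × F]

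| Non-users with any snippet (g) | π = 10% | π = 20% | π = 30% |
|---|---|---|---|
| 10% | 92% | 96% | 98% |
| 30% | 79% | 89% | 94% |
| 60% | 65% | 81% | 88% |
| 100% | 53% | 72% | 81% |

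Example, π = 10% and g = 100%: 0.0976 / (0.0976 + 0.90 × 0.0967) = 53%. With g = 10% the second term falls to 0.0087 and PPV is 92%.

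A more adverse setting (p0 = 0.50, five snippets, π = 10%, g = 100%) gives F = 0.333, S = 0.998 and PPV = 0.0998 / (0.0998 + 0.2996) = 25%.

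**Step 4. Prevalence alone, one snippet each.** With p0 = 0.30, a PPV of 90% becomes 84% if 20% of the target snippets show use, and 95% if 50% do. A shift in prevalence can move PPV either way.

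**Step 5. By arm.** The share of non-users falsely scored is g × F. In the scenario of Step 2 it is 0.10 × 0.097 = 1.0% when g = 10% and 9.7% when g = 100%. Text that raises g or k in one arm raises false use in that arm. The documents give neither quantity by arm, so the size of a spurious difference cannot be stated.

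**The case against.** The strongest reply is that a participant whose notes never mention a modality cannot be an NLP false positive for it. For rarely mentioned modalities g may be small, and the table then shows a PPV of 92% or more. That stands, and it is why the premise cannot be called false.

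The plan also has real safeguards. It tunes for PPV at the expense of sensitivity, tries to exclude history mentions, uses note type and timing as features, and drops NLP where the target is missed. Section 9.6 also compares self-report with record data. These lower the risk. None of them measures participant-level or by-arm PPV in the trial, and agreement between methods does not show which one is right.

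Three stronger readings are tempting but not supported:

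- **Participants are low users, so PPV must fall.** The exclusion allows up to two VA modalities, does not restrict non-VA use, and applies only at entry. Participants have a musculoskeletal claim and BPI severity of at least 4, which may make use more common than in VA-wide records.
- **Any mention counts as use.** Only snippets classified as current use count. That one suffices is an inference from the absence of a stated threshold.
- **The compounding is as steep as calculated.** Repeated notes on one patient tend to repeat wording, so errors are probably correlated and the effect of k smaller.

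**Conclusion.** The concern holds in a limited form. The planned validation does not establish that false positives are unlikely at the level at which use is scored. In the main scenario PPV runs from 53% to 98%, and in an adverse one it is as low as 25%. These figures rest wholly on assumed sensitivity, prevalence and snippet counts, on independent errors, and on a one-snippet rule. The share of non-users with any keyword snippet matters most.

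A reader might infer that false positives are in fact common, or that an effect on service use would be spurious. The documents show neither. The by-arm mechanism is plausible from the counselors' notes, but its size is unknown. The two primary outcomes do not use the NLP measure. This is an inexpensive improvement to a secondary outcome and mediator.

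**What to change.** 1. Draw part of the planned validation sample from study participants' own notes, of all types the algorithm will read, annotated blind to arm. Sample whole participant-periods, so that true use can be judged per person.
2. State the rule that turns snippets into a participant's score. Compute PPV per participant, modality and period, overall and by arm, and apply the existing 90% rule and fallback to that figure.
3. Exclude study counseling notes from the NLP corpus. Providers' replies to those notes will remain, which is why the by-arm check is still needed.
4. Add a sensitivity analysis in which an NLP positive alone does not count as use.

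Requiring two concordant positive notes is an option, not a necessity. Sections 3 and 4.3 should also be reconciled on snippets per modality (500 against 600 for validation).

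**Cost.** There will be fewer VA-wide training snippets and some loss of sensitivity, a trade Section 3 already accepts. Section 9.5.1 reports week-36 nail returns, so annotation may be finished; step 1 would then be extra work rather than reallocation. Precision is modest: around a PPV of 90%, the 95% half-width is 1.96 × √(0.9 × 0.1 / 100) = 6 points with 100 positive participant-periods and 8 points with 50. Rarer modalities may need pooling for the comparison by arm.
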